6.2.3.2. Mixed Model for Repeated Measures Analysis

MMRM analysis will be utilized to estimate the mean change from baseline in the monthly average number of CH attacks during the 12-week period after administration of the first dose of the IMP.

Postbaseline data will include data from three monthly analysis windows derived using the algorithm described in Section 6.1.3. Missing data will be handled as described in Section 6.1.4.2.

The MMRM will include baseline preventive medication use (yes or no), gender, region (US/Canada or other), treatment, month (months 1 to 3), and month-by-treatment interaction as

fixed effects and baseline number of CH attacks as a covariate. The unstructured covariance structure (UN) will be used to model intra-subject correlation. LS mean and SE for each treatment group, LS means and corresponding 95% confidence intervals for the treatment differences (fremanezumab - placebo), and the associated p-values from the overall results for treatment comparisons on the average of months 1 to 3 will be presented to support the primary analysis.

Example SAS codes for MMRM analysis:

```
PROC MIXED DATA=<name> METHOD=REML;
  CLASS USUBJID SEX BPMU REGION ATPTN TRTP;
  MODEL CHG=BASE BPMU SEX REGION TRTP ATPTN TRTP*ATPTN/S;
  REPEATED ATPTN/ SUB=USUBJID TYPE=UN;
  LSMEANS TRTP TRTP*ATPTN/ DIFF CL ALPHA=0.05;
  ODS OUTPUT LSMEANS= <name> DIFFS= < name>;
RUN;
```

Where TRTP denotes the planned treatment group; BPMU denotes the baseline preventive medication use (yes or no); CHG denotes the change from baseline; BASE denotes the baseline number of CH attacks; and ATPTN denotes the month or the analysis window.

The analysis will be performed on the FAS.

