2.4. Sample Size and Power Considerations

A sample size of 258 patients (86 evaluable patients completing the study per treatment group) will provide at least 90% power to detect a treatment difference of 4 CH attacks in the monthly average (assuming a common standard deviation [SD] of 8 CH attacks) at a 2-sided alpha level of 0.05. Assuming a 14% discontinuation rate, approximately 300 patients will be randomized in the trial.

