6.3.2. Mean Change from Baseline in the Number of Cluster Headache Attacks

The following 2nd and 3rd secondary efficacy endpoints will be analyzed based on the monthly average number of CH attacks using an MMRM method in a manner analogous to the analysis as described in Section 6.2.3.2.

- the mean change from baseline (run-in period) in the number of CH attacks during the 4-week period after administration of the first dose of the IMP, ie, based on week 0 to 4 data
- the mean change from baseline (run-in period) in the number of CH attacks during the 4-week period after administration of the third dose of the IMP, ie, based on week 8 to 12 data

Postbaseline data will include data from three 4-week analysis windows (weeks 1 to 4, weeks 5 to 8, and weeks 9 to 12) derived using the algorithm described in Section 6.1.3. Data will be

prorated to 28 days as the monthly average. CH attacks within each analysis window will be derived from the e-diary data as described in Section 6.1.1. Missing data handling methods are provided in Section 6.1.4.2

The analysis will be based on data from all three 4-week (monthly) analysis windows. Results for each endpoint will be subsetted from PROC MIXED outputs. For the 2nd secondary endpoint, the results from the first analysis window (weeks 1 to 4) will be presented; for the 3rd secondary endpoint, the results from the last analysis window (weeks 9 to 12) will be presented.

6.3.3. Mean Change from Baseline in the Weekly Average Number of Days with Use of Cluster-Specific Acute Headache Medications (Triptans and Ergot Compounds) During the 12-Week Period After Administration of the First Dose of the IMP

Use of triptans and ergot compounds for CH will be recorded in the e-diary. The 12-week period is the period from administration of the first dose of the IMP to the EOT/early withdrawal visit. The weekly average number of days with use of triptans or/and ergots for CH for a patient during 12-week period will be calculated and prorated to 7 days using formula [1B]. Missing data handling method is provided in Section 6.1.4.2.

Data will be analyzed using an ANCOVA method in a manner analogous to the primary endpoint as described in Section 6.2.2.

6.3.4. Mean Change from Baseline in the Weekly Average Number of Days Oxygen is Used to Treat Chronic Cluster Headaches During 12-week Period After Administration of the First Dose of the IMP

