7. MULTIPLE COMPARISONS AND MULTIPLICITY

Hochberg's step-up method will be implemented to test primary and secondary endpoints while controlling the overall type 1 error rate at 0.05.

The treatment comparisons will be for the fremanezumab 900-mg iv loading dose group versus placebo [H_{01}] and the fremanezumab 675-mg sc loading dose group versus placebo [H_{02}]. According to Hochberg step-up method, the rules of multiple comparisons for 2 null hypotheses for the primary endpoint are as follows:

1. If the resulting 2-sided p-values from both comparisons are ≤ 0.05 (reject both null hypotheses), then the next comparison of interest will be interpreted inferentially at the alpha level of 0.05 and statistical significance will be claimed for both active dose groups. Testing of secondary efficacy measures will be continued.
2. If the resulting 2-sided p-value from 1 of comparisons is > 0.05 (fail to reject the null hypothesis) and other resulting 2-sided p-value is ≤ 0.025 ($\frac{\alpha}{2} = 0.025$; reject the null hypothesis), then the result from the comparison with p-value ≤ 0.025 will be interpreted inferentially at the alpha level of 0.05, and statistical significance will be claimed for this active dose group. No further comparisons will be interpreted inferentially.
3. If the resulting 2-sided p-value from both comparisons are > 0.05 (fail to reject both null hypotheses), then no statistical significant will be claimed and no comparisons will be interpreted inferentially.

If the resulting 2-sided p-values from both comparisons for the primary endpoint are ≤ 0.05 (reject both hypotheses; case 1 as described above), testing of secondary efficacy measures will proceed at an error rate of 0.05 in the sequential manner as specified in Section 1.2. The same testing rules as described above will be followed. This process will continue either until all comparisons of interest for secondary endpoints are interpreted inferentially or until the point at which the resulting 2-sided p-value for a comparison of interest is > 0.05 . At the point where a 2-sided p-value > 0.05 , the testing process stops. No further comparisons will be interpreted inferentially.

For the last secondary endpoint (PPSI assessments), only the assessment at week 12 will be included in the multiple comparisons.

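### The repeated-measures model behind secondary endpoints 2 and 3 holds the baseline slope equal across months; a baseline-by-month term is a near-free safeguard on precision.

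*SAP*

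**What the plan says.** SAP 6.2.3.2 gives the MMRM in prose and in example code. The code reads "MODEL CHG=BASE BPMU SEX REGION TRTP ATPTN TRTP*ATPTN/S". The prose agrees: it lists treatment-by-month among the "fixed effects and baseline number of CH attacks as a covariate". On the covariance it says: "The unstructured covariance structure (UN) will be used to model intra-subject correlation". No baseline-by-month term appears there or elsewhere in either document. Protocol 9.5.4.3 says only that continuous endpoints will use ANCOVA or a repeated-measures mixed model.

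SAP 6.3.2 carries the model to two confirmatory endpoints: "The following 2nd and 3rd secondary efficacy endpoints will be analyzed based on the monthly average number of CH attacks using an MMRM method", by analogy with 6.2.3.2. It adds that "The analysis will be based on data from all three 4-week (monthly) analysis windows", with the month-1 and month-3 results then picked from the output. Under SAP 7, if both primary comparisons succeed, "testing of secondary efficacy measures will proceed at an error rate of 0.05 in the sequential manner as specified in Section 1.2", and testing stops at the first p-value above 0.05.

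**The concern.** One baseline slope serves three months. Suppose a patient's run-in count predicts month 1 better than month 3. The change from baseline then depends on baseline more steeply at month 3 than at month 1, and a single fitted slope lies between the two. The misfit goes into the residual variance of the months at the ends, which are the months that carry endpoints 2 and 3. With complete data, a separate ANCOVA for each month would estimate its own slope, so the restricted MMRM can be less precise than the simpler method that Protocol 9.5.4.3 also allows.

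What is at stake is power. A miss at endpoint 2 blocks endpoints 3 to 6, and a miss at endpoint 3 blocks endpoints 4 to 6. The MMRM sensitivity analysis of the primary endpoint and several exploratory analyses reuse the model, but they lie outside that sequence.

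**Working it through.** **1. The plan's own figure.** Inputs from SAP 2.4: difference 4, SD 8, two-sided alpha 0.05, power 90%, discontinuation 14%.

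- n per arm = 2 × (1.960 + 1.2816)² × (8/4)² = 84.06, so 85. The plan has "86 evaluable patients completing the study per treatment group".
- At 86: 4 / (8 × √(2/86)) = 3.279, and 3.279 − 1.960 = 1.319, which is power 90.6%.
- 258 / 0.86 = 300 randomized.

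The sample size reproduces. The plan states no SE or power for months 1 or 3.

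**2. Formula.** Let β_t be the true baseline slope at month t, S the residual covariance of the three months given baseline, and V the variance of baseline. In large samples with unstructured covariance:

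- fitted common slope b = 1′S⁻¹β / 1′S⁻¹1
- SE ratio at month t (common slope / baseline-by-month) = √(1 + V(β_t − b)²/S_tt) = √(1 + k²), where k = SD(baseline) × |β_t − b| / residual SD at month t

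The excess is 0.5% at k = 0.1, 2.0% at 0.2, 4.4% at 0.3 and 11.8% at 0.5. It is zero when the slopes are equal. Using change instead of raw counts subtracts 1 from every slope and leaves the ratio unchanged.

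**3. One case worked through (assumed).** AR(1) correlation 0.8 over baseline and three months, equal SDs.

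- Raw-count slopes are 0.8, 0.64 and 0.512.
- The weights 1′S⁻¹ are proportional to 0.84, 0.04 and 0.20, so b = (0.672 + 0.0256 + 0.1024)/1.08 = 0.741.
- Month 1: √(1 + 0.0593²/0.36) = 1.005, or 0.5% wider.
- Month 3: √(1 + 0.2287²/0.738) = 1.035, or 3.5% wider.
- Scaling so that the 12-week change has SD 8 gives a baseline SD of 11.0. The month-3 residual SD is then 9.77 with the common slope and 9.44 with separate slopes.
- Power for a difference of 4 at 86 per arm (applying the planning difference to month 3 is an assumption) is 76.6% and 79.3%.

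**4. Range.** The documents give no baseline SD, month-specific SD or baseline-to-month correlation, so each row is an assumption, scaled to SD 8 for the 12-week change.

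| Assumed structure | Month 1 SE excess | Month 3 SE excess |
|---|---|---|
| Compound symmetry, equal SDs | 0.00% | 0.00% |
| Compound symmetry 0.5-0.7, month SD falling or rising | 0.1-0.9% | 0.2-0.5% |
| Random intercept plus AR(1) | 0.3-0.5% | 1.1-1.7% |
| AR(1) 0.5-0.9 | 0.1-1.8% | 2.2-3.5% |
| AR(1) 0.6-0.8, month SD falling to 75% | 3.3-4.1% | 3.3-6.1% |

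For a difference of 4, the power given up is 0 to about 1 point at month 1 and 0 to about 3 points at month 3. The largest is 94.0% down to 91.1%, for AR(1) 0.8 with falling SD.

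**5. Check with dropout.** REML fits with unstructured covariance, 300 patients, 14% monotone dropout, 150 replicates per setting. The excess at months 1 and 3 was 1.3% and 3.1% for AR(1) 0.6, and 0.4% and 3.5% for AR(1) 0.8. With equal slopes (compound symmetry 0.5) the added term made the SEs about 0.1% larger. Bias hardly differed between the models: at month 3 under AR(1) 0.8 it was −0.162 with the common slope and −0.167 with separate slopes.

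**The case against.** The strongest case for leaving the plan alone is that a common-slope MMRM is valid and prespecified, and that nothing in the documents shows the slopes to differ. Protocol 2.1.1 justifies 12 weeks by fluctuating attack frequency, but that is an argument for a longer averaging period. Fluctuation around a stable patient level gives equal slopes and no loss. Baseline and each month are also counts prorated to 28 days, which smooths short-term variation. All of this stands, and it is why the point is conditional.

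A reader might infer three stronger things.

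- **That the loss could be large.** With residual SD 8, residual correlation 0.6, baseline SD 24 and slopes 0.2 apart per month, k = 24 × 0.2/8 = 0.6 and the SE is 17% wider, equivalent to about 36% more patients. The documents do not support that setting. The residual SD of the 12-week average would be 8 × √(2.2/3) = 6.85. If the planning SD of 8 describes the 12-week change, the average slope can be at most √(64 − 46.9)/24 = 0.17 in size. The month-1 slope would then be about zero or slightly positive, which contradicts the regression to the mean that motivates the worry. Against this, SAP 2.4 does not say whether its SD is before or after baseline adjustment, and entry requires at least 10 run-in attacks with no upper limit. A wide baseline spread is therefore possible but not shown.
- **That the omission undermines the handling of missing data.** This was not demonstrated. The dropout simulation showed no material difference in bias.
- **That the whole efficacy analysis is affected.** The primary ANCOVA has one outcome per patient. The MMRM sensitivity analysis reports the average over months, where the excess was about 1% at most in the structures examined.

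**Conclusion.** The restriction is real and reaches two alpha-controlled endpoints. Its cost is conditional: zero if the baseline slope is the same each month, and otherwise about 0-4% on the month-1 SE and 0-6% on the month-3 SE over the assumed structures. It would be more if baseline spread is large relative to the residual SD. The conclusion rests on those assumed correlations and on reading the planning SD of 8 as the SD of the 12-week change. It concerns efficiency only: with complete randomized data the treatment difference is unbiased either way. This is a minor improvement, worth making because it is so cheap.

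**What to change.** Before unblinding, add BASE*ATPTN to the MODEL statement and the prose of SAP 6.2.3.2, and so to 6.3.2. The LSMEANS statements need no change, because the treatment differences do not depend on the baseline value at which they are evaluated. For consistency the term may also go into the exploratory MMRMs that reuse the model (6.4.2 to 6.4.5, and those in 6.4.9).

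The cost is one parameter fewer than the number of time points: 2 with three months, and 11 in the twelve-week models of 6.4.2 and 6.4.5. In the three-month model the SE is about 0.1% larger if the term is not needed. The subgroup fits of endpoints 2 and 3 (SAP 6.2.4) would inherit the term, and small subgroups would pay somewhat more for it. No new data are required.

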6.2.4. Subgroup Analyses

The following subgroup analyses will be performed for primary endpoint and selected secondary endpoints (mean change from baseline in the number of CH attacks [the 2nd and 3rd secondary endpoints]; mean change from baseline in the number of days with use of cluster-specific acute headache medication [the 4th secondary endpoint]; mean change from baseline in the number of days oxygen is used [the 5th secondary endpoint]):

- Age group (< 40 and ≥40 years old)
- Race group (white and other)
- Sex (male and female)
- Baseline preventive medication use (yes and no)
- Region (US/Canada and other)

Data will be analyzed in a manner analogous to the method described in the section for each of these endpoints.

Modification to SAS codes: adding a ‘by’ statement for the subgroup variable; If the subgroup variable is in MODEL statement, remove the subgroup variable from MODEL statement accordingly.

The subgroup analyses will be performed on the FAS.

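### The subgroup analyses give a separate result in each level but plan no estimate or test of whether the treatment effect differs between levels

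*SAP*

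**What the plan says.** SAP 6.2.4 names five factors, each with two levels: age, race, sex, baseline preventive medication use and region. They apply to the primary endpoint and to the second to fifth secondary endpoints, on the full analysis set (FAS). The method is given by reference: "Data will be analyzed in a manner analogous to the method described in the section for each of these endpoints". The only change to the code is to add a BY "statement for the subgroup variable; If the subgroup variable is in MODEL statement, remove the subgroup variable from MODEL statement accordingly". In SAS this fits an unconnected model in each level.

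The parent analyses (SAP 6.2.2 for the ANCOVA, 6.2.3.2 for the MMRM) present LS mean differences from placebo with 95% CIs and p-values. By analogy, so does each subgroup level.

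No comparison between levels appears anywhere. The ANCOVA has main effects only, and the MMRM's only interaction is treatment by month. SAP Section 7 confines formal testing to the two whole-group comparisons on the primary endpoint and then the listed secondary endpoints. Protocol Section 9 plans no efficacy subgroup analysis. Neither document says how the subgroup p-values should be read.

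**The concern.** The usual question for a subgroup analysis is whether the effect is consistent. Sex and preventive medication use are stratification factors, and both, with region, are in the primary model, so readers will ask that question of them.

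The planned display offers two p-values side by side. A within-level p-value depends on the size of the level as well as on the effect in it. Two levels with the same true effect can easily fall on opposite sides of 0.05, especially if one is small. A reader may then report that the drug works in one group and not in the other, when the data show no such thing.

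**Working it through.** **Inputs.** SAP 2.4 gives 86 evaluable patients per arm, a target difference of 4 attacks per month, two-sided testing at 0.05 and power of 90% or more. On variability it reads "assuming a common standard deviation [SD] of 8 CH attacks". The share of patients in each subgroup level is not in the documents. I assume 50/50 to 90/10, with the same split in every arm.

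**The plan's own figure.** The standard error of a difference is σ√(2/n) = 8 × √(2/86) = 1.220. Power is Φ(4/1.220 − 1.96) = Φ(1.319) = 0.906, or 0.903 with the noncentral t. The stated power of at least 90% reproduces. So does the sample size: 258/(1 − 0.14) = 300.

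**Same true effect (4) in both levels.** Apply the same formula within each level to get powers p1 and p2. The levels contain different patients, so the results are independent and

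P(exactly one level has p≤0.05) = p1(1 − p2) + p2(1 − p1).

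At 50/50, n = 43 per arm, SE = 8 × √(2/43) = 1.725 and power = Φ(4/1.725 − 1.96) = 0.640. Then 2 × 0.640 × 0.360 = 0.461.

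At 70/30, 0.783 × 0.565 + 0.435 × 0.217 = 0.537.

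**Between-level contrast.** The standard error of the difference between the two effects is 8√(2/n1 + 2/n2). At 50/50 this is 2.440, so the 95% CI half-width is 1.96 × 2.440 = 4.78. Power for a true effect of 4 in one level and 0 in the other is about Φ(4/2.440 − 1.96) = 0.374.

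| Split | n per arm, larger / smaller | Power, larger / smaller | Exactly one p≤0.05 | CI half-width for difference in effects | Interaction power, 4 versus 0 |
|---|---|---|---|---|---|
| 50/50 | 43 / 43 | 0.640 / 0.640 | 0.461 | 4.78 | 0.374 |
| 60/40 | 51.6 / 34.4 | 0.719 / 0.545 | 0.480 | 4.88 | 0.362 |
| 70/30 | 60.2 / 25.8 | 0.783 / 0.435 | 0.537 | 5.22 | 0.324 |
| 80/20 | 68.8 / 17.2 | 0.835 / 0.311 | 0.627 | 5.98 | 0.259 |
| 90/10 | 77.4 / 8.6 | 0.875 / 0.178 | 0.742 | 7.97 | 0.166 |

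**Simulation check** (t-tests, 6,000 trials per split, equal effects). Exactly one level was significant in 46%, 55% and 64% of trials at 50/50, 70/30 and 80/20. A treatment-by-subgroup test on the same data gave a false signal in 4.7%, 5.1% and 4.8%.

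**Sensitivity.** The FAS keeps early withdrawals with at least 10 diary days, so it may be nearer 100 per arm. The figures at 50/50, 70/30 and 80/20 are then 42%, 51% and 61%. With 86 per arm and a true effect of 3 they are 49%, 52% and 56%; with a true effect of 2 they are 33%, 34% and 35%.

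**The case against.** The strongest reply is that the information is already there. The two levels of a factor are fitted on different patients, so anyone can subtract the two estimates and take √(SE1² + SE2²) as the standard error. At 50/50 that is √(1.725² + 1.725²) = 2.440, the same as in the working. This stands. A reader might infer that the planned output cannot address consistency; it can, and what is missing is a pre-specified and displayed contrast.

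A reader might also infer that the trial's error rate is inflated. The documents do not support that. Subgroup results lie outside the sequence in SAP Section 7, and no text says that significance in one level only will be read as a difference. Any misuse would be the reader's, although the plan does not guard against it.

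It is tempting to count the p-values: 5 factors × 2 levels × 2 regimens × 5 endpoints = 100, of which about 5 would fall below 0.05 if there were no effect at all. That is a separate multiplicity point. The 100 are strongly dependent, and an interaction test would still leave 50 contrasts.

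Nor is fitting separate models in small levels a material fault. Separate models avoid assuming equal residual variance across levels.

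Finally, an interaction test is weak here. That also stands, and it is why the estimate with its CI matters more than the p-value.

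**Conclusion.** The point holds as a modest gap in the subgroup plan. SAP 6.2.4 specifies within-level results that are valid in themselves and omits the one quantity that speaks to whether effects differ. Under the plan's design assumptions for the primary endpoint, reading the paired p-values against each other would suggest a difference that does not exist in about 46% of trials at 50/50, 54% at 70/30 and 63% at 80/20. A direct test would do so in about 5%.

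These figures rest on assumed splits, equal splits across arms, a normal approximation and no gain from covariates. The effect of 4 and SD of 8 are stated only for the monthly attack average, so the figures should not be carried over to medication or oxygen days. The primary analysis and the confirmatory error rate are not in question.

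**What to change.** In SAP 6.2.4, for each factor add one model on the FAS: the planned terms plus subgroup and treatment-by-subgroup. Sex, preventive use and region are already main effects, so only the interaction is new for them. For the MMRM endpoints also add subgroup-by-month and treatment-by-subgroup-by-month, and take the contrast at the month that defines the endpoint.

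Report, for each regimen, the between-level difference in treatment effect with its 95% CI and an interaction p-value labelled exploratory. Show these alongside the level-specific LS mean differences with CIs. State that within-level p-values will not be used to claim different effects, and that a non-significant interaction will not be read as proof of consistency.

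The cost is a few lines of text and code, with no new data and no change to the primary analysis. The pooled model assumes common covariate effects and a common residual variance across levels. The interaction test has only about 17% to 37% power for an effect of 4 versus 0, with CI half-widths of about 4.8 to 8.0 attacks, so it will often be inconclusive.
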